#### **4.5.2 Inclusion criteria for COVID-19 associated myocarditis/pericarditis**

1. COVID-19 infection within the previous 42 days.

AND

2. Myocarditis/pericarditis as per Brighton Criteria for vaccine associated myocarditis/pericarditis.

AND

3. No alternative cause of presentation.

#### **4.5.3 Inclusion criteria for MIS-C/A myocarditis/pericarditis**

1. Brighton case definition for MIS-C/A (Level 1 to 3b).

AND

2. Myocarditis/pericarditis as per Brighton Criteria for vaccine associated myocarditis/pericarditis.

AND

3. No alternative cause of presentation.

#### **4.5.4 Inclusion criteria alternative etiology myocarditis.**

1. Myocarditis/pericarditis as per Brighton Criteria for vaccine associated myocarditis/pericarditis.

AND

2. No alternative cause of presentation.

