## 4.3 Study population

The study population will include any patient with:

1. Vaccine associated myocarditis/pericarditis.
2. COVID-19 myocarditis/pericarditis.
3. MIS-C/A myocarditis/pericarditis
4. Alternative etiology myocarditis.

Patients will be required to satisfy the inclusion and exclusion criteria. Eligibility waivers to the inclusion/exclusion criteria are not permitted.

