## 4.5 Inclusion criteria

### 4.5.1 Inclusion criteria for vaccine associated myocarditis/pericarditis.

1. COVID-19 vaccination within previous 42 days.

AND

2. At least one cardiac symptom of suspected myocarditis/pericarditis (Appendix 5).

OR

At least two non-specific symptoms (Appendix 5).

OR

In infants and young children, at least two non-specific pediatric symptoms (Appendix 5).

OR

No symptoms, but abnormal histopathology or a combination of abnormal cardiac biomarkers with abnormal cardiac imaging (echo or MRI).

AND

3. At least one of the following objective findings (Brighton Criteria case definitions, Appendices 1 to 5):
  - a. Histopathologic examination of myocardial tissue (autopsy or endomyocardial biopsy) showed myocardial inflammation.
  - b. Elevated myocardial biomarker (Troponin T, Troponin I, or CK-MB).
  - c. Cardiac MRI abnormality.
  - d. Echocardiographic abnormality.
  - e. New or worsening arrhythmia on electrocardiogram, Holter monitor, or telemetry.
  - f. Elevated inflammation biomarkers: ESR, CRP, hs-CRP, or D-Dimer.
  - g. Physical examination pericardial friction rub or pulsus paradoxus.
  - h. Pericardial fluid or inflammation by imaging (echo, MRI, or CT).
  - i. Enlarged heart on chest radiograph.

AND

4. No alternative cause of presentation. e.g. infectious or autoimmune myocarditis.

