#### **4.6 Exclusion criteria**

- For prospective invitation and follow-up, inability to provide informed consent. Consent will be sought from patients or their authorised substitute decision maker.
- Patients not fulfilling Brighton Criteria levels 1-3 will be excluded if they are level 4 (insufficient evidence for myocarditis) or Level 5 (not myocarditis) or have an alternative diagnosis such as myocardial infarction.

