### **5. VISIT SCHEDULE AND PROCEDURES**

Consenting patients will be followed up clinically by their regular physician (e.g. Cardiologist, Internist, other physician) in collaboration with their local site-PIs, in accordance with the 2022 ACC/AHA standard of care guidelines for the management of myocarditis.

Patients will be followed at 3 months and 12 months after diagnosis and annually thereafter for up to 3 years. To standardize follow-up timing the date of vaccination will be assigned as the baseline date. However, baseline visit data will be collected from initial presentation and medical contact which is usually the date of diagnosis. This distinction is made because there is a variation between cases in date of vaccination to date of diagnosis/initial presentation.

The case report form variable list (Appendix 7) outlines the essential elements to be collected including demographic data, vaccination status, presenting symptoms, physical examination findings, diagnostic testing (routine laboratory work, electrocardiogram, MRI), treatments, and patient outcomes. Quality of life, depression, anxiety, and physical activity will be measured at baseline, 3 months, 12 months, and annually thereafter using validated instruments: quality of life EQ-5D-5L questionnaire for adults or EQ-5D-Y questionnaire for children; depression PHQ-9 and anxiety GAD-7; physical activity International Activity Questionnaire. These will be conducted at clinical visits or by telephone if no concurrent clinical visit is scheduled.

Baseline data will be collected for all etiologies of myocarditis, but thereafter follow-up visits will only be undertaken for patients with vaccine associated myocarditis/pericarditis, COVID-19 myocarditis/pericarditis, and MIS-C/A myocarditis/pericarditis (i.e. not alternative etiology myocarditis).

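### Section 4.5.4 defines the alternative-etiology group by the absence of an alternative cause, so it can bar the cases the group is named for, and it does not keep the group separate from the vaccine group.

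*Protocol*

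**What the plan says.** Section 4.3 names four populations, the last being "4. Alternative etiology myocarditis", and adds that "Eligibility waivers to the inclusion/exclusion criteria are not permitted".

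Section 4.5.4 gives that population two criteria. The first is myocarditis or pericarditis by the Brighton definition. The second reads "2. No alternative cause of presentation". No exposure is named, and recent vaccination, COVID-19 infection and MIS-C/A are not excluded.

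The same closing criterion appears in 4.5.1, 4.5.2 and 4.5.3. In each of those it follows a named exposure or syndrome: vaccination within 42 days, COVID-19 infection within 42 days, or the MIS-C/A definition. Only 4.5.1 says what the phrase covers: "4. No alternative cause of presentation. e.g. infectious or autoimmune myocarditis".

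Section 4.6 uses related but different wording. It excludes patients who "have an alternative diagnosis such as myocardial infarction".

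On follow-up, section 5 states: "Baseline data will be collected for all etiologies of myocarditis, but thereafter follow-up visits will only be undertaken for patients with vaccine associated myocarditis/pericarditis", together with the COVID-19 and MIS-C/A groups. It then spells out the exclusion: "i.e. not alternative etiology myocarditis".

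**The concern.** In 4.5.1 to 4.5.3 the last criterion does a clear job. It removes cases that another cause explains better than the named exposure. In 4.5.4 there is no named exposure, so the word alternative has nothing to refer to. The line appears to have been carried over from the other groups.

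Two things are at stake. The first is who enters: a site that applies the meaning given in 4.5.1 will refuse an autoimmune or viral myocarditis, while a site that goes by the group's name will enrol it. With waivers barred, a site cannot properly settle this case by case. The second is assignment: if one patient can satisfy the criteria of two groups, the protocol does not say in which group that patient belongs.

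**Working it through.** No arithmetic applies, because the protocol gives no target number, event count or precision for group 4. The check is to apply the criteria to typical cases under the two meanings of the phrase that the protocol itself offers.

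- **Reading A**, from 4.5.1: another cause of myocarditis, such as infection or autoimmune disease, is barred.
- **Reading B**, from 4.6: only a diagnosis that is not myocarditis, such as infarction, is barred.

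| Case | 4.5.4, reading A | 4.5.4, reading B | 4.5.1 |
|---|---|---|---|
| Brighton level 1–3, autoimmune or other infectious cause identified, no recent vaccination | refused | admitted | not met |
| Brighton level 1–3, no cause identified, no recent vaccination | admitted | admitted | not met |
| Brighton level 1–3, vaccinated within 42 days, no other cause | admitted | admitted | met |
| Brighton level 1–3, vaccinated within 42 days, autoimmune cause identified | refused | admitted | not met |
| Presentation explained by infarction | refused | refused | not met |

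Row by row:

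1. On reading A the patients for whom the group is named are refused. On reading B they enter.
2. Unexplained cases enter on both readings. They belong in the group, so on reading A the group is incomplete; what it does hold is not misplaced.
3. The vaccine case satisfies 4.5.1 and 4.5.4 on both readings. Nothing in 4.5.4 removes it, so the two groups are not mutually exclusive.
4. A recently vaccinated patient with an autoimmune cause is turned away by item 4 of 4.5.1. On reading A that patient is turned away by 4.5.4 as well and, absent COVID-19 or MIS-C/A, has no group.
5. Infarction is kept out on both readings, and 4.6 excludes it in any case.

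The overlap in row 3 is stated for the vaccine group because it is certain there. On reading B it extends to COVID-19 and MIS-C/A cases. On reading A it depends on whether COVID-19 itself counts as an infectious cause, which the text does not settle.

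On which reading the text favours: 4.5.4 repeats the cause wording of 4.5.1, whereas 4.6 speaks of a diagnosis. Reading B would also leave item 2 with little to do, since Brighton levels 2 and 3 in Appendices 1 and 3 already require that no other diagnosis explains the symptoms (level 1 does not), and 4.6 excludes such cases. Against that, section 5 refers to all etiologies at baseline and Appendix 7 records the etiology of the myocarditis. Both suggest that identified causes were meant to be included.

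**The case against.** The strongest reply is that the infectious-or-autoimmune example stands only in 4.5.1, where its job is to support attribution to the vaccine, and it is not repeated in 4.5.2 to 4.5.4. Elsewhere, in 4.6 and in the pericarditis definition of Appendix 3, the alternative is a condition such as infarction or pulmonary embolus. On that view the target patients enter and the group's name shows the intent. This stands in part: the refusal of identified causes holds on one reading, not on all. It does not remove the overlap with 4.5.1.

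One could go further and take the phrase, in this group, to mean no cause among vaccination, COVID-19 and MIS-C/A. That may be what was meant, and it would separate the groups, but 4.5.4 does not say it.

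A second reply is that little depends on group 4, since no objective in 3.1 or 3.2 and no endpoint in 3.3 or 3.4 names it. That is correct, and it limits the consequence.

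A reader might also infer that following this group only at baseline is an error, or that the group therefore contributes no information on MACE. The documents do not support either inference. The three primary objectives name only the other three groups, section 4.10 times follow-up extraction from those three diagnoses, and section 5 excludes group 4 from follow-up visits explicitly. That is a consistent choice of scope. Baseline data on this group can include MACE components present at presentation, since Appendix 7 lists ventricular function, arrhythmia and death, and Appendix 8 marks events at baseline. What is absent is a complete 30- or 42-day rate. Section 3.3 counts those days from vaccination, so the clock does not apply to patients without an index vaccination.

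**Conclusion.** Item 2 of 4.5.4 is wrong as written. With the only explanation of the phrase that the protocol gives, it refuses identified infectious and autoimmune cases and keeps only unexplained ones. With the narrower meaning taken from 4.6, those cases enter. On either meaning a case within 42 days of vaccination with no other cause satisfies both 4.5.1 and 4.5.4.

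The size is limited. What is affected is the composition of group 4, its baseline description and the assignment of cases to groups. No planned endpoint analysis of the other three groups uses group 4 as a comparator. The number of patients affected cannot be derived: the protocol gives neither the share of cases with an identified cause nor a target for this group. The conclusion rests on the text alone and on no assumed rate. A statement that the group holds the wrong patients altogether would go too far, since unexplained cases are legitimate members and the refusal of identified causes depends on the reading.

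**What to change.** Replace item 2 of section 4.5.4 with wording to this effect: *Does not meet 4.5.1, 4.5.2 or 4.5.3; cause other than COVID-19 vaccination, COVID-19 infection or MIS-C/A, whether identified (e.g. other infectious, autoimmune) or idiopathic; no non-myocarditis/pericarditis diagnosis explaining the presentation (see 4.6).*

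The first clause makes group 4 exclusive of the other three. The second admits both identified and unexplained causes. The third keeps the function that 4.6 already serves.

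The cost is one criterion in one section, with the ethics approval that section 4.13.6 requires for any amendment. No visits, data items or follow-up are added. Charts already placed in group 4, or refused for it, should be checked once against the new wording.

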#### **4.6 Exclusion criteria**

- For prospective invitation and follow-up, inability to provide informed consent. Consent will be sought from patients or their authorised substitute decision maker.
- Patients not fulfilling Brighton Criteria levels 1-3 will be excluded if they are level 4 (insufficient evidence for myocarditis) or Level 5 (not myocarditis) or have an alternative diagnosis such as myocardial infarction.

#### **4.7 Case identification**

##### **4.7.1 Provincial and territorial adverse event following immunization (AEFI) reporting.**

The Public Health Agency of Canada will connect us with all provincial and territorial public health authorities to discuss collaboration. Public health partners will be invited to a priority-setting exercise (along with other key stakeholders) to refine the data collection protocol, outcomes and analyses, and identify priorities. Several public health units are already counting on this study to provide follow-up for these patients as the individual units do not have the capacity to do so.

##### **4.7.2 Collaborating networks.**

COVID-VIHPR. This is a CIHR funded study to elucidate the potential underlying mechanisms of the pathogenesis of mRNA vaccine myocarditis, and incorporates very detailed imaging, biospecimen and immunological analysis with controls also exposed to the vaccine. This study is not intended to be a broad comprehensive registry. However, the patients in COVID-VIHPR will contribute relevant data into the MYCOVACC surveillance study. Funding from MYCOVACC will support the longer term follow up of these patients.

POPCORN, IMPACT, and SIC. We have been coordinating closely with the pediatric teams led by [name] (POPCORN, IMPACT, and SIC). IMPACT is able to identify patients but they offer no follow-up of the patients identified. Thus, MYCOVACC is the only infrastructure able to follow the patients longitudinally.

#### **4.7.3 Electronic health records**

Patients will be identified by chart review of health records at participating sites by research teams led by site investigators according to their local guidelines and standard operating procedures. The study will be promoted through multiple communication channels of the Canadian Cardiovascular Society, including websites, emails, newsletters, and social media channels.

#### **4.8 Cohort time period**

The cohort entry start date is December 1, 2020. This date corresponds to the first authorization of mRNA vaccine in Canada by Health Canada (Pfizer BioNTech on December 9, 2020). The cohort entry end date will be determined by renewal of funding for the surveillance study by the Public Health Agency of Canada.

#### **4.9 Ethical considerations**

The study will be carried out in accordance with the World Medical Association Declaration of Helsinki (1964) and its revisions. Favourable ethical opinion will be sought from Research Ethics Committee (REC) in all jurisdictions where the study will be conducted. Patients will only be allowed to enter the prospective study once they have provided written informed consent. The PI will be responsible for updating the REC of any new information related to the study.

#### **4.10 Retrospective chart review**

The retrospective study will identify previous cases of vaccine associated myocarditis/pericarditis, COVID-19 associated myocarditis/pericarditis, MIS-C/A myocarditis/pericarditis, and alternative etiology myocarditis.

Recruiting clinicians will refer patients presenting with myocarditis/pericarditis since December 1, 2020 to research staff (i.e., the date Health Canada approved the first mRNA vaccine for COVID19). Initial chart review to determine eligibility for the study and subsequent chart review for initial presentation and follow-up time points will be completed. As vaccination for COVID-19 and COVID-19 infections are occurring continually, chart review of eligible patients will follow the same structure as patients identified from December 1, 2020.

The same clinical information as the prospective study will be collected, including presentation, clinical bloodwork, and cardiac imaging. No data will be collected for the purposes of this study that has not already been collected as part of routine follow-ups. Only available data will be extracted. Follow-up data will be extracted from charts using standardized chart extraction forms at 3 months, 12 months, and annually for up to 3 years following the date of diagnosis of vaccine associated myocarditis/pericarditis, COVID-19 myocarditis/pericarditis or MIS C/A myocarditis/pericarditis.

#### **4.11 Retrospective chart review waiver of consent**

Waiver of consent is requested for retrospective chart review. Retrospective chart reviews are usually confined to a specific timeframe. However, this study has been commissioned by the Public Health Agency of Canada as a surveillance study for a new and unique disease entity for which our understanding is continually evolving and which has significant implications for vaccine confidence and public health. We therefore request permission to perform retrospective chart review of routine clinical care on an ongoing basis for the duration of the study.

#### **4.12 Prospective follow-up invitation**

The invitation to participate in prospective follow-up will follow local standard operating procedures as approved by the Research Ethics Committee in each participating centre, specific to the jurisdiction and patient circumstances. Invitation procedures may include:

1. For patients attending a care provider for standard clinical care, the care provider will provide information regarding the study and ask permission for the research team to contact the patient.
2. For patients who have previously provided general consent to contact for research of any form, which has been documented in the health record, the research team will contact the patient.
3. For patients not attending a care provider nor with previously documented consent to contact, an invitation letter to receive further information regarding the study will be sent by mail or email by the research coordinator with approval of the primary care provider.

4. The invitation letter will include a registration telephone number and be available in English and French languages. The invitation for contact will include an option for the potential participant to contact the participating site to opt out of the study. Otherwise, a research coordinator will follow-up by telephone to discuss the study within 2 weeks.

#### **4.13 Consent process**

The Principal Investigators will retain overall responsibility for the informed consent of participants at their site and will ensure that any person delegated responsibility to participate in the informed consent process is duly authorized, trained and competent to participate according to the ethically approved protocol, principles of Good Clinical Practice (GCP) and Declaration of Helsinki.

The consenting process will be undertaken with one of two methods: Conventional 'in person' written consent and E-Consent. Assenting patients will be given the option of what form they would like to consent to the study. This is to ensure that patients unable or unwilling to complete an e-consenting process are not disadvantaged.

A copy of the consent form will be given to the patient, care giver, or parents. Copies will be filed in the study record and in the patient's primary healthcare record. e-consenting will also be used if deemed appropriate by study team. The original consent form or completed e-consent form will be filed in the study file and sites will be required to scan and upload the consent forms into a secure study database for each consented patient.

Where a participant is required to re-consent or new information is required to be provided to a participant, the PI will ensure this is done in a timely manner. The right of a participant to refuse participation without giving reasons will be respected. The PI takes responsibility for ensuring that all vulnerable subjects are protected and participate voluntarily in an environment free from coercion or undue influence.

##### **4.13.1 Conventional written consent**

The process of conventional 'in-person' consent will involve:

- A discussion between the potential participant and an individual knowledgeable about the study about the nature and objectives of the study, and possible risks associated with their participation.
- The presentation of written material to read and digest (e.g., patient information sheet and consent document which must be approved by the REC and be in compliance with GCP, local regulatory requirements and legal requirements).
- The opportunity for potential participants to ask questions.
- Potential participant will then be able to sign the consent form or decline to give their consent.

##### **4.13.2 Virtual electronic consent**

- Following verbal consent and collection of electronic contact details, potential participants will be sent an electronic consent form (via REDcap) for their review.
- They will then review audio-visual and written information about the study – which will include information on the objectives of the study and outline any possible risks associated with taking part. This information (e.g., patient information sheet, electronic multimedia resources consent document which must be approved by the REC and be in compliance with GCP, local regulatory requirements and legal requirements)
- Potential participants will be given the opportunity to ask any questions about the study either directly or at a later time.
- The e-consent form can then be signed and electronically returned to the study team or the participant can decline to give their consent.

##### **4.13.3 Mental Capacity**

A person is assumed to have the mental capacity to make a decision unless it is shown to be absent. Mental capacity is considered to be lacking if, in a specific circumstance, a person is unable to make a decision for him or herself because of impairment or a disturbance in the functioning of their mind or brain. Patients that are unable to provide informed consent will not be included in this study. Where a participant is able to consent but later becomes incapacitated, they will be withdrawn from the trial.

An assent form will be used for children up to but not limited to 13 years of age and for those 14 and older with limited mental capacity. Local REB guidelines and SOPs will be followed at participating sites.

#### **4.13.4 Withdrawal criteria**

Participants may withdraw consent to the study at any time without giving reasons and without prejudicing any aspect of standard clinical care. When withdrawal is requested, the study team will clarify the level of withdrawal and offer a pre-determined tiered list of options to the patient:

- Complete withdrawal with no further in person visits, no virtual visits, no active data collection, and no outcome follow-up using administrative data.
- Withdrawal with no in person visits, no virtual visits, and no active data collection, but continued outcome follow-up using administrative data.
- Withdrawal with no in person and no virtual visits, but continued active data collection and outcome follow-up using administrative data.
- Withdrawal with no person visits, but continued virtual visits with active data collection and outcome follow-up using administrative data.

